A minimum of 93 participants (31 participants per group) aged 4-to-13 will be recruited through convenience sampling, consented, and randomized by staff to one-of-three preparation programs (VR, mock MRI, or booklet). Details of the comparison groups are outlined in **Table 4**. Given the restricted availability of the simulator, child life specialists, and the availability of participants, we are unable to fully randomly allocate participants. As such, participants will be randomly assigned to the intervention options available according to their individual availability (using Research Randomizer <https://www.randomizer.org/>). For example, if a participant is available on a Thursday that virtual reality and booklet are available, they will be randomly allocated to one of these interventions.

This phase will have open recruitment to all children and adolescents interested in participating, such that participants may not be BCCH patients scheduled for an MRI. This recruitment strategy was selected due to the resource constraints associated with limiting the evaluation group to MRI patients only.

Table 4. Details of the comparison groups.

	VR Simulation	MRI Preparation Booklet	Mock MRI
Facilitator	Research Assistant	Research Assistant	Child Life Specialist
Location	BCCH	BCCH	Simulation Room
Content	Refer to The Virtual Reality Simulation	Refer to MRI Preparation Book	Individualized intervention in physical simulator.

The different interventions will be held in separate private rooms located in BCCH, such that the VR and booklet groups will not have prior exposure to the imaging centre or the simulation room in advance of their assessment. This is to simulate our intended delivery in hospital, medical office, or clinic settings but minimize alternative explanations associated with testing in the simulation room where assessments will take place (previously described in **Table 3**).

Data will be collected throughout the implementation process (**Figure 3**). The predictive variables (demographics and relevant history, and delivery type) will be captured at the start of the session. The primary outcome variable is likelihood of success (pass/fail) of the MRI simulation, and will be measured at the end of the assessment. Anxiety will also be measured at three time points. Usability testing will be conducted throughout to capture possible quality improvements and amendments to each of the program delivery modes.

Inclusion/Exclusion Criteria

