Participants must be between the ages of 4-to-13 years to be included in the evaluation.

The following exclusion criteria, which have been noted in previous studies conducted using virtual reality programs, will be adopted for this project:

- mental disability (content not appropriate)
- significant visual and auditory impairment (this program focuses on auditory and visual cues)
- inability to speak or understand English (content and study staff are English speaking)
- history of seizures or epilepsy (triggered by virtual reality)
- facial or head wounds (cannot wear the virtual reality headset)

Implementation Plan

[figure not shown]

Figure 3. Implementation process.

The testing phase of the implementation process, depicted in Figure 3 will be completed over two hours, and will involve the following steps:

- 1) Participants and parents/guardians are greeted by staff and enter the intervention room.
- 2) Staff will obtain written consent from parents and verbal assent from children (5 minutes).
- 3) Participants will complete the Venham Picture Test (VPT) with staff (pre-test). In parallel, parents will complete the Short STAI on the iPad. (5 minutes)
- 4) Staff will reveal the allocated delivery mode (VR, mock MRI, or booklet) to the participant and explain the procedure.
- 5) Staff will ask participants to indicate on the Smileyometer how good they think the intervention is going to be.^{30,31} This will give a measure of expectation that can indicate whether or not the participant is subsequently let down by the activity or pleasantly surprised.
- 6) Staff will measure the participant's interpupillary distance using sliding calipers.
- 7) Participants will be given 45 active minutes to engage with the intervention. Groups include:

Group 1 (VR): The VR group will receive a virtual reality simulation designed during Phase 1 of this study.

Group 2 (mock MRI): The mock MRI will be provided by the CLS, according to the current care plan which consists of exposing children to the mock MRI, medical devices, and procedures. The mock MRI is located within the BCCH medical imaging facility.

Group 3 (booklet): The standard MRI preparation booklet group will provide access to a series of printed photos and text showing the MRI experience step-by-step to help prepare for the MRI.

- 8) Participants will be asked to indicate on the Smileyometer how good they actually thought the activity was overall (1 minute).

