- 9) Participants will be informed that they will now be completing a simulation test with the MRI scanner. Participants will be reminded of their free and informed ongoing consent.
- 10) The participant will be transferred to the simulation room, located in the medical imaging center at BCCH. Upon entering the simulation room, participants will verbally complete the VPT with staff (during test). In parallel, parents will complete the Short STAI on the iPad. (5 minutes)
- 11) Participants will be guided through a mock MRI and be assessed using MoTrack®, an objective head motion tracking system.³² The simulation will be completed over 20 minutes and will involve progression through the “MRI procedure”, remaining in the bore for 8 minutes. All participants will receive the same type of simulated scan. We will not be simulating any invasive procedures that can sometimes occur during the MRI (i.e. an IV or intravenous contrast liquid). Please note that this assessment involves a mock procedure using the simulator, not a real MRI.
- 12) Immediately following the simulation, participants will verbally complete the VPT with staff (post-test). In parallel, parents will complete the Short STAI on the iPad. (10 minutes).

- 13) Users will be asked to indicate on the *Smileyometer* how they thought the preparation activity was overall in preparing them for the MRI. Parents/guardians will be asked to complete the USE Questionnaire.
- 14) Staff will ask the user open-ended questions on the preparation materials according to three separate criteria of fun, ease of use, and how good it was for learning about the MRI experience. The final usability assessment will take a total of 10 minutes.
- 15) After the session is "complete", children will be told that they "happen to have some time left" so they can play with any of the preparation materials offered (VR, Mock MRI, Booklet) for 5-minutes if they want to "because they did so well during the activity." This will give children a natural choice selection and will be used to gauge preferences for the activities.
- 16) A verbal session debrief will include an opportunity for questions to mitigate any residual feelings of discomfort or anxiety that may arise from the project's activities.

Outcome Measures

The measures used to evaluate the intended outputs and outcomes associated with this project are outlined below (**Table 4**).

Table 4. Outputs and outcomes associated with the project.

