The predictive success in avoiding sedation will be measured using Motrak® software assessment. MoTrak® uses a sensor attached to the participant's head to determine the position of the head in space relative to a transmitter located within the simulator. The sensor records angular rotations as well as positional displacements from an initially calibrated position. This information is displayed and logged by the program in real-time, allowing objective observation of head motion in an MRI simulator.³² The fail threshold is set at 3mm of movement in any of the positional displacements (x,y,z), which is in accordance with imaging protocols at the Hospital.

Child Anxiety: Venham Picture Test – 5 minutes

Anxiety assessment with children will be completed in pictorial form to better adapt to the cognitive and communicative abilities and styles of younger children. The Venham Picture Test has been well-validated in children for assessing procedural anxiety^{33,34}, and comprises eight cards which two figures on each card, one anxious character and one non-anxious character. The children will be asked to point at the figure they feel most like at that moment. All cards will be shown in their number order. If the child points at the anxious figure, a score of one is recorded and if the child points at the non-anxious character, they will be given a score of zero. Children will complete the at three timepoints (before, during, after the mock MRI).

Secondary Measures

Parental Anxiety: Short State-Trait Anxiety Inventory (Short STAI) – 5 minutes

Anxiety assessment with parents/guardians and children at baseline, after completing the intervention, and before the mock MRI. The Short STAI is a 6-item, adapted version of the well-validated Spielberger State-Trait Anxiety Inventory Scale.³⁵ It distinguishes between general proneness to anxious behavior rooted in the personality and anxiety connected to a current state, and has been validated for use in children.³⁵

Demographics and Relevant History

Demographic and possible confounding information (age, sex, prior experience with medical imaging, experience with virtual reality, type of mobile phone) will be obtained through a data collection form. Data will be de-identified using a participant identification number.

Length of Stay (LoS)

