For the purposes of this evaluation, we will define total LoS as the duration, in minutes, from starting the *preparation* segment to completion of the simulated *assessment*. Inter-segment times will also be recorded. Preparation time will be capped at 45 minutes. Assessment time will be capped at 20 minutes. Start of preparation will be noted as time when study staff finish describing the intervention and indicate it is time to begin the active preparation. Time will stop when the participant is “discharged” from the MRI simulation, before the natural choice selection exercise and debriefing process begins. Time spent transitioning between activities or breaks required for reasons unrelated to the evaluation will not be counted towards overall LoS.

Interpupillary Distance

Interpupillary Distance will assume normal conditions and be measured objectively before preparation using Pryor's (1969) method³⁶ to ensure appropriate set up of the virtual reality device.

[figure not shown]

FIG. 1. Formula for interpupillary distance.

Usability Testing

The Smileyometer – 1 minute

The Smileyometer^{30,31} is an instrument used for measuring the opinions of technology in children, and has been validated in multiple studies assessing educational materials and software. The Smileyometer is based on the Visual Analogue Scale,³⁷ consisting of a 5-point Likert scale that uses pictorial representations. Participants are asked to point to the face they relate to.

Guided Survey – 10 minutes

The RA will ask the participant several open-ended questions on the preparation materials according to three separate criteria of fun, ease of use, and how good it was for learning about the MRI experience.

USE Questionnaire – 10 minutes

The USE Questionnaire²³ will be administered to the parents/guardians after the mock MRI only. This will allow participants to compare the VR application to the “effective MRI” experience. The USE Questionnaire is a 7-point Likert rating scale that has been well-validated to assess a program’s usefulness, ease-of-use, ease of learning, and satisfaction.

Analysis and Interpretation

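### The plan does not say who guides the scored mock scan, what they may say, or who sees the live motion display, so coaching could differ by arm and move the pass/fail primary outcome

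*Combined protocol and SAP*

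**What the plan says.** All references are to section 4.4 of the combined protocol and SAP unless stated.

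- **Outcome.** "The primary outcome variable is likelihood of success (pass/fail) of the MRI simulation, and will be measured at the end of the assessment". Under Predictive Success in Avoiding Sedation, a displacement of 3 mm on any of the three axes is a fail.
- **Conduct of the scored scan (step 11).** "Participants will be guided through a mock MRI", with head motion tracked by sensor. The guide's role is not named. Some standardisation is stated: "All participants will receive the same type of simulated scan", with 20 minutes in total and 8 minutes in the bore.
- **Motion display.** Of the tracking output: "This information is displayed and logged by the program in real-time". The text does not say who can see it.
- **Who prepares the child.** In the mock MRI arm, "The mock MRI will be provided by the CLS, according to the current care plan". The table of comparison groups gives a Research Assistant as facilitator for VR and for the booklet.
- **Who knows the arm.** Staff randomise the child and reveal the allocation (step 4). Staff also give the Venham test on entry to the simulation room and straight after the scan (steps 10 and 12).
- **Later contact.** In the Guided Survey, "The RA will ask the participant several open-ended questions".

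The readable text mentions no masking of any session role, no script for the scored scan, and no rule on prompts, recalibration or restarts.

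**The concern.** Staying still is a behaviour, and it responds to what a child is told while lying in the bore. A timely reminder can turn a fail into a pass without any error in the measurement. If reminders, reassurance or restarts are offered more freely in one arm, the difference will be read as an effect of the preparation method.

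Two features of the plan make such a difference possible. Session staff know the allocation, and the preparing facilitator is a different professional in one arm. Nothing prevents that facilitator from also guiding the scored scan.

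The comparison of VR with mock MRI is the most exposed, because section 4.2 predicts no difference there: uneven coaching could create a difference or hide one. Section 4.5 then takes the predicted non-sedation rates into the cost-effectiveness modelling, so any bias would carry forward. Coaching that was not recorded cannot be adjusted for in the analysis.

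**Working it through.** **1. What is standardised and what is not.**

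| Element of the scored scan | In the readable text |
|---|---|
| Type of scan, total time, time in bore | Same for all arms (step 11) |
| Scoring rule | 3 mm on any axis, recorded by sensor |
| Who guides the child | Not named |
| Whether the guide knows the arm | No masking described; session staff know it |
| What may be said, and when | Not stated |
| Recalibration or restart | Not stated |
| Who sees the motion display | Not stated; output is shown live |

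The first two rows protect the scoring and the exposure. The other five leave open how the child is handled while the outcome is being produced.

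**2. Size, for illustration.** The documents give no figure for the effect of prompting, so the share of failures rescued is an assumption.

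- Base rate: 283/344 = 82% (Table 2, section 3.0). This is conversion to non-sedated MRI after simulation, not the simulator pass rate.
- Formula: rise in pass rate = (1 − p) × share of would-be failures rescued, with prompting in one arm only.
- Share 25%: 0.18 × 0.25 = 0.045, or 4.5 points.
- Share 50%: 0.18 × 0.50 = 0.09, or 9 points.
- In an arm of 31: 31 × 0.045 = 1.4 children, and 31 × 0.09 = 2.8 children.

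Sensitivity to the base rate: the simulator pass rate in the same table is (283 + 8)/344 = 84.6%. The rise is then 0.154 × 0.25 = 3.9 points to 0.154 × 0.50 = 7.7 points.

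**3. What a shift of that size does to a two-arm comparison.** Assume 31 per arm, a true pass rate of 82% in both arms, and a two-sided 5% pooled test of two proportions. The plan does not name this test; it serves only to scale the problem. Write d for the shift and p̄ for the mean of the two rates.

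- SE under the null: s0 = √(2p̄(1 − p̄)/31). Critical difference: c = 1.96 × s0.
- SE under the shift: s1 = √(p1(1 − p1)/31 + p2(1 − p2)/31).
- Rejection probability = 1 − Φ((c − d)/s1) + Φ((−c − d)/s1).

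For d = 0.09: p̄ = 0.865, s0 = 0.0868, c = 0.170, s1 = 0.0860, giving 17.7%. For d = 0.045: p̄ = 0.8425, s0 = 0.0925, c = 0.181, s1 = 0.0923, giving 7.7%. Exact binomial enumeration gives 18.5% and 7.9%. The nominal rate is 5%.

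The plan's total of 93 is used here only for the arm size; this point does not dispute it.

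**The case against.** **The outcome is measured objectively and the scan is the same for everyone.** Both are true and deserve credit. They remove scoring bias and unequal exposure, but neither governs what is said to the child while motion is recorded.

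**The case rests on silence.** This stands, and it limits the wording. A reader might infer that the guide is unmasked, that no script exists, or that the familiar specialist runs the scored scan in the mock MRI arm. The documents do not say so. They leave the guide unnamed and describe no masking or script, and Figure 3, which shows the implementation process, is not available. A reader might also infer that the guide or child watches displacement build towards 3 mm. The text says what the program displays, not who sees it.

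**The size is speculative.** This largely stands. Prompting in one arm only is an extreme case. If any 3 mm displacement is a fail, a reminder helps only when it comes before that point. The text also does not show that motion in the roughly 12 minutes outside the bore (20 − 8) is scored. A reader might infer that uneven coaching could produce or hide most of the 20% effect cited in the sample size paragraph. That is not supported: from 82% the largest illustrated shift is 9 points, under half of 20. Coming close to 20 needs a much lower base rate, such as 62% (82 − 20, not a figure in the plan), with half of failures rescued in one arm only: 0.38 × 0.50 = 19 points.

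**Having a research assistant run every scored scan would settle it.** It would not. A Research Assistant prepares the VR and booklet children, so barring only the specialist would move the familiarity imbalance to the other arms. The Guided Survey shows an assistant asking questions; it does not show that a second person is available to run the simulator.

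**Conclusion.** The concern holds as a gap in the conduct of the primary assessment: the plan as written permits coaching during the scored scan to differ by arm. It does not show that this will happen, or in which direction.

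Under the stated assumptions the pass rate in one arm would rise by about 4.5-9 points from 82%, roughly one to three children in 31. That would lift a nominal 5% false-positive rate to about 8-18%. The result depends on the assumed rescue shares, on prompting in one arm only, and on a base rate borrowed from conversion to non-sedated MRI.

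The sponsor should make the change before data collection. Confidence is moderate, because most of the premises are omissions and two figures could not be read.

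**What to change.** In step 11:

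1. Use one fixed script, with the same prompts at the same times, in all three arms.
2. Allow no feedback or prompting triggered by the motion display during the 8 minutes in the bore.
3. Keep the display out of the guide's and the child's view, and let the software log.
4. Record every unscripted prompt, recalibration or restart, and report them by arm.
5. Name the role that guides the scored scan and apply any restriction to all arms alike. Where existing staffing allows, whoever prepared the child, specialist or research assistant, does not guide that child's scored scan. Where it does not, record who guided.

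If Figure 3 or a site procedure already covers any of this, bring it into the text of step 11.

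**Cost.** Items 1 to 4 need a short script, a repositioned screen and a log sheet, with no extra staff. Item 5 may need a second person in some sessions. The documents do not show that one is available, and they report limited access to the simulator and specialists, so it is conditional on staffing. The scored scan would be slightly less like routine specialist-led practice.

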Measure	Immediate Outputs	Intended Outcome
Primary		
MoTrak®	# of participants "prepared" to be scheduled for an effective MRI	
Improve access to MRI preparation for children who:
 
 - Live out of town - Would like to practice skills at home - Have mobility issues 
Improve non-sedation rates for MRI scans.

Venham Pictoral Test & Short STAI	# of participants with reduced anxiety # of parents with reduced anxiety	
Improve access to MRI preparation materials.
 
Improve behavioral compliance during medical procedures.

Secondary		
Smileyometer	# of participants who find the delivery mode fun and engaging to use	
Improve acceptability of preparation materials.
 
Improve satisfaction.

USE Questionnaire	# of parents who find the preparation materials useful	
Improve acceptability of preparation materials.
 
Improve satisfaction.

Natural Choice Selection	# of participants who select the booklet # of participants who select the mock MRI # of participants who select virtual reality # of participants who select none	Identify preference for engaging. Identify frequency of contact and time engaging.
Length of Stay	Minutes spent per segment	Improve hospital efficiency
Guided Survey	# of participants who find the booklet fun, easy to use, and good for learning about the MRI experience # of participants who find the mock MRI fun, easy of use, and good for learning about the MRI experience # of participants who find the virtual reality game fun, easy of use, and good for learning about the MRI experience	Improve utility of MRI preparation materials. Identify frequency of contact and time engaging.
Interpupillary Distance	Average interpupillary distance per age	Improve headset configuration.

Primary Measures

Predictive Success in Avoiding Sedation

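### The plan gives three different sets of primary outcomes (one, two or three measures) and no rule for choosing between them

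*Combined protocol and SAP*

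**What the plan says.** All of the relevant text is in the combined protocol and SAP, mostly in section 4.4.

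- **Design text** (just before the inclusion and exclusion criteria): "The primary outcome variable is likelihood of success (pass/fail) of the MRI simulation, and will be measured at the end of the assessment". The next sentence, "Anxiety will also be measured at three time points", gives anxiety no rank.
- **Outcome Measures table** (the second Table 4): the primary block holds a MoTrak row and a row labelled "Venham Pictoral Test & Short STAI", both above the secondary divider. The anxiety row counts "of participants with reduced anxiety # of parents with reduced anxiety", so children and parents are scored separately.
- **Measures text**: the Primary Measures heading covers the MoTrak assessment and "Child Anxiety: Venham Picture Test – 5 minutes". The heading "Secondary Measures" follows, and its first entry begins "Parental Anxiety: Short State-Trait Anxiety Inventory (Short STAI".
- **Analysis and Interpretation**: alpha 0.05 and 90% power appear as inputs to the sample size of 93. One sentence then combines simulator pass/fail with three anxiety time points in a repeated-measures ANOVA by delivery type. The subsection gives no order of testing, alpha split or criterion for success.
- **Section 4.2, hypothesis 2a**: VR and booklet are expected to differ in outcomes, and no outcome is named.

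**The concern.** The three statements cannot all hold, and the Short STAI is explicitly primary in one place and secondary in another. The choice decides how the trial reads. Suppose VR lowers anxiety relative to the booklet but does not raise the simulator pass rate. Under the table that is a positive primary result; under the design text it is not. Because hypothesis 2a names no outcome, a difference on any listed primary could be reported as confirming it. If the choice is made after the data are seen, the 5% error rate used in planning no longer describes the primary claim.

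**Working it through.** **Step 1. Count the primaries in each place.**

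| Place in section 4.4 | MoTrak pass/fail | Venham (child) | Short STAI (parent) | Primaries |
|---|---|---|---|---|
| Design text | primary | no rank | no rank | 1 |
| Outcome Measures table | primary | primary | primary | 3 |
| Measures text | primary | primary | secondary | 2 |

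MoTrak is the only measure that is primary in all three. The disagreement between the design text and the measures text rests on a sentence and on headings, so it does not depend on how the table was extracted.

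**Step 2. Does the sample size show which outcome governs?** Inputs from Analysis and Interpretation: 3 groups, 3 time points, effect size 0.2 (read as Cohen's f), alpha 0.05, power 90%, dropout 10%. The correlation between repeated measures (rho) and the sphericity correction (epsilon) are not given. For the within-between interaction, with noncentrality f² × N × 3 × epsilon / (1 − rho):

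- rho 0.5, epsilon 1 (assumed software defaults): N = 67, rounded to 69 for equal groups; 69/0.9 gives 77. This is not 93.
- rho 0.37 to 0.38, epsilon 1: N = 84 for equal groups; 84/0.9 gives 94, and 84 × 1.1 gives 93.
- rho 0.5, epsilon 0.75: the same 84, then 93 to 94.
- rho 0.30 to 0.31 with no dropout allowance: 93.

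The figure is under-specified rather than shown to be wrong. It also points both ways: the effect size is justified by sedation rates, which belongs with pass/fail, while the model has three time points, which belongs with anxiety. It does not settle which outcome is primary.

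**Step 3. False-positive risk, if each primary were tested at 0.05.** For k independent tests the chance of at least one false positive is 1 − 0.95^k:

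- k = 1: 5.0%
- k = 2: 1 − 0.9025 = 9.75%
- k = 3: 1 − 0.857375 = 14.3%

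Whatever the dependence, the bound for three tests is 3 × 0.05 = 15%. Simulation of three equally correlated two-sided normal tests gives about 12.5% at correlation 0.5 and 8.4% at 0.9. The documents give no correlations, so these are a range. Positive correlation between child anxiety, parent anxiety and movement seems likely.

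**Step 4. What follows for power if pass/fail is the sole primary.** This is an illustration for two arms, two-sided 0.05, pooled-variance normal approximation. It assumes that the 82% non-sedated conversion in section 3.0 (283/344) can stand for a pass rate and that the planned effect is 20 percentage points.

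- 82% against 62%, 31 per arm: null standard error √(2 × 0.72 × 0.28 / 31) = 0.1140; alternative standard error √((0.1476 + 0.2356) / 31) = 0.1112; z = (0.20 − 1.96 × 0.1140) / 0.1112 = −0.21; power about 42%.
- 28 per arm (31 less 10%): about 38%.
- 75% against 55%: about 38% at 31 per arm and 34% at 28.
- 70% against 50%: about 36% and 33%.

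Under these assumptions 90% power for 82% against 62% would need 104 per arm.

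**The case against.** **The conflict is partly loose terminology.** The design text ranks an outcome variable, while the table and headings group instruments. The Venham test is primary in both the table and the measures text, so it conflicts only with the singular wording of the design text. This has some force, but it does not help with the Short STAI, and a design text that names one primary outcome is not compatible with two or three.

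**The work is developmental.** The introduction speaks of exploring effectiveness, and the project is framed around technology readiness and refining a prototype. Against that, section 4.2 states comparative hypotheses and the sample size claims 90% power, so readers will expect a defined primary result.

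**Stronger readings that the documents do not support.**

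- A reader might infer that the plan permits success on any one of three tests. It contains no success rule and does not set out three separate tests. What can be said is that nothing rules such a claim out.
- A reader might infer that every outcome is tested at 0.05. That level appears only in the power calculation. The Smileyometer and USE data are summarised descriptively and the guided survey is coded for themes.
- A reader might count two arm contrasts per outcome and quote 1 − 0.95^6 = 26.5%. That requires six independent tests, but contrasts that share the VR arm are correlated. Hypothesis 2b also predicts no difference between VR and mock MRI, so a significant result there would count against it. The inflation applies to hypothesis 2a only.
- A reader might infer that 93 already includes an alpha split, since alpha 0.05/3 with rho 0.5 gives 84 and then 93 to 94. The text states 0.05, and other unstated choices give the same total.

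**Conclusion.** The inconsistency is real and is in the current text: the primary set has one, two or three members depending on where one looks, and no testing order, adjustment or success rule resolves it. For a claim that VR differs from booklet, the chance of at least one false positive would be 5%, 9.75% or 14.3% for one, two or three primaries. These figures assume that each outcome is tested at 0.05 and that the tests are independent; with positive correlation the three-outcome figure is lower, and 15% is the ceiling. The contradiction itself rests on no assumption. It should be settled before any comparison of outcomes by group.

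Relabelling alone is not enough. The only inferential model in the analysis text is built on three time points, and a single pass/fail result taken at the end of the assessment cannot be its outcome.

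**What to change.** 1. Keep MoTrak pass/fail as the single primary outcome, as the design text already says.
2. In the Outcome Measures table, move the Venham and Short STAI row to the secondary block. In the measures text, move the Venham test under the secondary heading. Report the p-values of both as secondary and unadjusted.
3. In Analysis and Interpretation, name pass/fail for VR against booklet as the primary analysis, with a method for a binary outcome (for example, a comparison of proportions or logistic regression). Keep the repeated-measures ANOVA for the anxiety scores as a secondary analysis.
4. State which outcome the 90% power refers to, and give the assumptions behind it.

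Keeping all three as primary would also resolve the conflict, provided that a rule is written down in advance, for example Bonferroni at 0.05/3 = 0.0167 each. The pass/fail outcome would still need its own method.

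**Cost.** No new data or procedures are needed. The anxiety results lose primary status, and the stated power may become less favourable: under the illustrative rates above it is about 33% to 42% for pass/fail at 28 to 31 per arm, against the 90% now claimed.
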